### **Adverse event assessment**

See sections 13 and 14 for details on AE and SAE reporting and assessment

At each study visit patients will be asked to report any untoward medical occurrences and will also be specifically questioned regarding the presence of:

- Myopathic symptoms (weakness, muscle pain)
- Gastrointestinal disturbance (diarrhoea, nausea, vomiting, abdominal pain)
- Jaundice

## **11.1 Calculations**

### **Framingham Risk Score**

Ten-year risk of developing “hard” coronary heart disease endpoints (myocardial infarction and coronary death) will be calculated based on the Framingham Risk Score using an online calculator available at [www.old.mdcalc.com/framingham-coronary-heart-disease-risk-score-si-units/](http://www.old.mdcalc.com/framingham-coronary-heart-disease-risk-score-si-units/)

### **D.A.D Risk Score**

The D.A.D equation is a cardiovascular risk assessment model that is tailored for use in HIV positive participants, taking into account exposure to specific PIs, family history of CHD and previous, as well as current smoking status. A D.A.D. risk score will be calculated on all

participants at baseline to allow for a comparison with the FRS and to compare each measure with cIMT. The calculation will be performed using an online tool available at: <http://www.cphiv.dk/tools/dadriskequations/tabid/437/default.aspx>

### **Body Mass Index (BMI)**

A BMI will be calculated at screening visit and at the forty-eight (48) and ninety-six (96) week visits. Height will only be measured at screening and assumed to remain stable through the study period

$$\text{BMI} = \text{Weight (kg)} / \text{height}^2 \text{ (m)}$$

### **Creatinine clearance**

An estimated creatinine clearance will be calculated at screening visit to determine eligibility for entry into the trial using the Cockcroft-Gault equation

$$\text{For men } Cl = \frac{1.23 \times \text{weight (kg)} \times (140 - \text{age (years)})}{\text{Creatinine } (\mu\text{mol/L})}$$

$$\text{For women } Cl = \frac{1.03 \times \text{weight (kg)} \times (140 - \text{age (years)})}{\text{Creatinine } (\mu\text{mol/L})}$$

## **11.2 Laboratory Assessments**

### **Handling of Biological samples**

All biological samples (excluding those for storage and testing of innate immunity) will be processed at the Alfred Hospital laboratory or the Swiss site; local laboratory reference ranges will apply (see appendix 22.3 and 22.4).

Biological samples for testing of innate immunity will be handled at the Burnet Institute. Plasma will be separated and frozen (-80°C). Plasma markers will be analysed on batched frozen samples by ELISA.

Swiss sites will store plasma samples (6mls per visit) at -80°C and ship to the HUG cardiology laboratory for testing of plasma markers. Innate immunity markers (PBMC) will not be performed at Swiss sites.

A separate laboratory SOP will be provided to all the Swiss sites.

### **HIV specific testing**

HIV monitoring (CD4+ T-cell count and HIV viral load) will be performed at screening, baseline and weeks 12, 48, 72 and 96

### **Laboratory assessments for safety**

Routine laboratory assessments for safety and tolerability will be performed including:

- Full Blood Examination (FBE)
  - o Consisting of; Haemoglobin (Hb), total White Cell Count (WCC), Lymphocyte Count (Lymp), Neutrophil Count (Neut) and Platelet count (Plt)
- Biochemistry
  - o Consisting of; Sodium (Na), Potassium (K+), Chloride (Cl), Bicarbonate (HCO3), Calcium (Ca), Phosphate (PO4), Urea (Ur), Creatinine (Cr) and creatinine phosphokinase (CPK)

- An estimated glomerular filtration rate (eGFR) based on the Modification of Diet in Renal Disease (MDRD) equation is calculated electronically by the AH laboratory and will be recorded
- Liver Function Tests: Total Protein (TP), Albumin (Alb), Bilirubin (Bil), Alanine aminotransferase (ALT), Alkaline phosphatase (ALP) and Gamma-glutamyl transpeptidase (GGT)
- Pregnancy screen in women with child bearing potential (at screening visit); Beta Human chorionic gonadotrophin ( $\beta$ -HCG)

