## 5 Flow Chart

Assessment	Screen	Baseline	Post randomization				
Week	-4	0	12	24	48	72	96
Written Informed consent	X						
Inclusion / exclusion criteria	X						
Demographic questionnaire a	X						
Physical examination b	X	X			X		X
Compliance assessment c					X		X
Weight & Height measurement d	X				X		X
Adverse event assessment e		X	X	X	X	X	X
Risk Score Calculation f	X						
Laboratory Assessments							
T Cells	X		X	X	X	X	X
HIV RNA viral load	X		X	X	X	X	X
FBE g	X	X	X	X	X	X	X
Biochemistry h	X	X	X	X	X	X	X
Fasting Lipids/glucose i	X	X		X	X		X
hsCRP		X	X				X
Research Blood samples j		X	X		X		X
Structural assessments							
Carotid IMT k	X				X		X
Pulse Wave Velocity l	X				X		X

a Demographic data, medical history and medication questionnaire (will be performed with a trained interpreter if required)

b Includes blood pressure measurement, cardiovascular examination; electrocardiogram (ECG) at screening visit only

c See appendix 17.2: Compliance self-assessment questionnaire and visual analogue scale

d Height will only be measured at screening visit. Body Mass Index (BMI) will be calculated at screening and 12 and 24 month post randomisation

e Unscheduled visits may be performed for safety/tolerability concerns

f Framingham (FRS) and Data Collection on Adverse Events of Anti-HIV Drugs (D.A.D) risk scores calculated

g Full Blood Examination: Haemoglobin, White cell count, Lymphocyte count, Neutrophil count, Platelet count

h Including sodium, potassium, bicarbonate, chloride, calcium, phosphate, urea, creatinine; Liver function tests (LFTs): alanine aminotransferase (ALT), alkaline phosphatase (ALP), total protein, albumin; creatinine phosphokinase (CPK), pregnancy screen in women with child bearing potential

i Participants will fast overnight and have bloods taken in the morning for total cholesterol (TC), low-density lipoprotein cholesterol (LDL), high-density lipoprotein cholesterol (HDL), triglycerides (TG) and glucose

j Blood for markers of innate immunity and inflammation; see Section 11.2 for full description of testing to be performed and stored bloods for future projects

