### 9.5 Pregnancy

Women of child-bearing potential will be screened for pregnancy on admission to the study. Due to a lack of study data relating to the effects of statins on pregnant woman and/or the foetus those who are found to be pregnant will be excluded from study participation and referred to an appropriate medical service.

Female participants will be advised to avoid pregnancy while participating in the study. Women who become pregnant after randomisation will be withdrawn from the trial but will continue to be monitored for the development of adverse events (AE) or serious adverse events (SAE).

*For Switzerland: Women of childbearing potential must use two reliable contraceptive methods during the entire trial, from day 1 to one month after the end of the trial. Accepted methods are hormonal methods such as the birth control pill associated with a barrier method such as the preservative.*

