#### Assessments

1. Demographic data, medical history and medication questionnaire to be completed
2. Full physical examination including:
  - a. Height and weight
  - b. Assessment of peripheral pulses
  - c. Blood pressure
  - d. ECG
3. Laboratory assessments
  - a. FBE and biochemistry
  - b. Beta HCG for all women of child bearing potential
  - c. Fasting metabolic assessment
  - d. HIV viral load and CD4+ T cell count (and percentage)
4. Structural assessments
  - a. cIMT
  - b. cPWV (\*Melbourne Participants only)
5. Calculations
  - a. BMI

- b. Creatinine clearance
- c. FRS
- d. D.A.D. risk score

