  - a. Creatinine clearance <50 ml/min (calculated using the Cockcroft-Gault equation)
  - b. Transaminase (ALT, AST) above 3 times upper normal limit
  - c. Acute hepatic failure
  - d. Compensated cirrhosis Child Class B or C

If the patient fulfils all eligibility criteria (1-26 above) then a baseline visit will be booked. CRFs from participants assessed but found to be ineligible for inclusion in the study will be entered into the database recording the reason for ineligibility.

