#### **12.5 Baseline visit**

Participants will be required to present to the study site having fasted overnight for at least 12 hours (no food, caffeine or caloric drinks; free water is encouraged)

Assessments performed:

1. Targeted physical examination and updated history, assessment for new concomitant medications
2. Adverse event assessment
3. Laboratory assessments
  - a. Biochemistry
  - b. Fasting metabolic assessment
  - c. hsCRP
  - d. Markers of innate immunity and inflammation
  - e. Storage of plasma and PBMCs (\*Melbourne participants only) for possible further analysis in the future

Patients will be provided with a three (3) month supply of the study medication and educated regarding possible clinical signs of potential adverse events (muscle ache, fever, abdominal pain, jaundice, rash); regardless of randomisation. Patients will also be provided with contact details for study co-ordinators in case of adverse event.

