### **12.1 Withdrawal visit**

For participants that fulfil any of the withdrawal criteria above a withdrawal visit is performed if the participant agrees. All assessments made during the withdrawal visit can be recorded on the CRF (unscheduled visit). This visit will include, but is not limited to, a targeted medical review and physical examination, laboratory examination for safety reasons (chemistry and haematology), pregnancy test for women and study drug return. Tests performed can vary according to the judgement of the study physician.

Clinical or biological abnormalities perceived at the withdrawal visit will be followed at an interval decided by the study physician, until they are resolved or baseline values obtained.

Participants that withdraw from the study may be contacted by telephone at study end for vital status, unless they refuse and this is documented.

In Australia: In the event of withdrawal of consent by the participant, the Form for withdrawal of participants is completed.

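### The first study-drug supply can be handed over on a pregnancy test up to four weeks old, and no text makes dispensing wait for a baseline result

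*Combined protocol and SAP*

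**What the plan says.** On the timing of the test:

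- **Section 11.2, Laboratory assessments for safety.** A bullet of its own reads "Pregnancy screen in women with child bearing potential (at screening visit". The Biochemistry bullet in the same list spells out its components, and beta-HCG is not among them.
- **Section 12.1 Screening, Assessments.** Item 3b is "Beta HCG for all women of child bearing potential". Item 3a, listed separately, covers FBE and biochemistry.
- **Section 12.1 Withdrawal visit** (the number is used twice). After chemistry and haematology it adds, as a separate item, "pregnancy test for women and study drug return".
- **Section 5 Flow Chart, footnote h.** The definition of Biochemistry includes a "pregnancy screen in women with child bearing potential". The Biochemistry row is marked at every visit, baseline included.
- **Section 9.5.** "Women of child-bearing potential will be screened for pregnancy on admission to the study". No visit is named.

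On eligibility and first dispensing:

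- The flow chart row "Inclusion / exclusion criteria" is marked at screening only, and section 12.3 ends: "If the patient fulfils all eligibility criteria (1-26 above) then a baseline visit will be booked".
- The section 12.2 on time windows puts baseline within four weeks of screening.
- The baseline laboratory list in section 12.5 has biochemistry, fasting metabolic tests, hsCRP, immune markers and storage. The section then says "Patients will be provided with a three (3) month supply of the study medication", with no condition.

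**The concern.** The protocol treats pregnancy as a contraindication to statin use (exclusion 15a in section 9.2) and as a reason for withdrawal (section 9.4). Section 9.5 gives as its reason the lack of data on statin effects in pregnancy. That standard matters most when exposure starts, at the baseline visit. If the only test is at screening, a woman who conceives afterwards can leave baseline with three months of study drug and no scheduled test first; her next scheduled visit is week 12.

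The texts also disagree, so two sites could each follow the protocol and test differently. The matter is one of participant safety. It has no bearing on sample size, error rates or the primary cIMT analysis.

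**Working it through.** The plan states no figure to reproduce. The check sets the relevant texts side by side and applies the visit window.

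**1. Scheduled tests up to and including baseline, per woman of child-bearing potential**

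| Source followed | Screening | Baseline | Total |
|---|---|---|---|
| 11.2 with section 12 | 1 | 0 | 1 |
| Flow chart footnote h | 1 | 1 | 2 |

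The Biochemistry row is marked at screening and weeks 0, 12, 24, 48, 72 and 96, which is 7 visits. Two of these fall at or before first dispensing.

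**2. How far the silence of 12.5 can be pressed.** Not far on its own. The flow chart marks FBE at baseline and 12.5 omits it, so the section 12 lists are not complete. The liver tests are not named in 12.5 either, so Biochemistry there must already carry them. The conflict therefore rests on the explicit timing in 11.2 and the separate listing in 12.1 (Screening), supported by the wording for the withdrawal visit, against footnote h. Section 9.5 does not settle it.

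**3. Age of the newest result at first dispensing.** Section 12.1 has all screening procedures done at one visit, so the sample dates from that visit. The longest interval to baseline is 4 weeks × 7 days = 28 days. Under 11.2 and section 12 the newest result is therefore 0 to 28 days old at dispensing.

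**4. Texts that make first dispensing wait for a baseline pregnancy result.** None, on either reading. Under footnote h blood could be drawn and capsules handed over at the same visit before the result is known.

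**5. Any other step at baseline that confirms status.** Eligibility is marked once, at screening, and no re-check at baseline is described. Section 12.5 asks for updated history and new medications, and the baseline form asks about new diagnoses; neither confirms a negative status.

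**6. Case report forms.** Pregnancy has 2 entries on the screening forms (a question row and a checklist item). It has none among the baseline rows available to this review, some of which are cut short. This carries little weight: the baseline form has no result row for any laboratory test, and section 19.1 lists self-reported pregnancy status as source data, so the screening question may not record an assay at all.

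**The case against.** The strongest answer is that a baseline test is already planned. Footnote h includes it in Biochemistry, the flow chart marks Biochemistry at baseline, and 12.5 lists Biochemistry. Since that term in section 12 must already be read broadly enough to take in the liver tests, it can be read to take in the pregnancy screen too. This is a fair reading, and it would be wrong to say that the protocol as a whole lacks a baseline test. It does not remove the contradiction with the timing written in 11.2, and it does not make dispensing depend on the result.

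A second argument is that no baseline laboratory result gates dispensing in this protocol, CK and transaminases included, so a gate for beta-HCG is a preference. It is true that the documents contain no such rule to breach. The case for the gate is that the protocol itself excludes pregnant women and the check is cheap.

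Third, there are safeguards: the screening test, advice to avoid pregnancy, the baseline history, and in Switzerland two contraceptive methods. They lower the chance of a missed pregnancy. The Swiss rule starts on a day 1 that is not defined. Melbourne, with 72 of the 102 planned participants, has only the advice. A pregnancy the woman does not yet know of would pass the history questions.

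Finally, the order of sections 12.4 and 12.5, and the randomisation number on the screening form, suggest that randomisation precedes baseline. A gated test could then leave a woman randomised but never dosed. That stands as a detail for the fix to cover.

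**Conclusion.** The point holds. A site following 11.2 and section 12 can dispense the first 3-month supply on a pregnancy test up to 28 days old, with one scheduled test by that point instead of the two implied by footnote h. Under both readings, no text ties first dispensing to a baseline result.

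The protocol should be changed, though the practical size is uncertain and may be small: neither the number of women of child-bearing potential nor a chance of conception between visits is given, so no expected number of exposed pregnancies can be calculated. The consent form and the separate Swiss laboratory SOP were not available to this review and might say more. Confidence is medium. Testing after baseline is outside this point.

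**What to change.** 1. **Section 12.5:** add beta-HCG for women of child-bearing potential to the laboratory list, with a negative result required before study medication is dispensed.
2. **Section 11.2:** extend the stated timing to screening and baseline.
3. **Section 9.5:** replace the reference to admission with screening and baseline, before first dispensing.
4. **Flow chart footnote h:** name the visits at which the pregnancy screen is done, at minimum screening and baseline. Whether it is repeated later is for the sponsor to state.
5. **Baseline case report form:** add a beta-HCG result row above the row that records the 3-month supply.
6. **Handling of a positive result:** state whether randomisation waits for the baseline test. If it does not, state how a woman with a positive result is withdrawn, followed and counted, since the efficacy set in section 17 requires at least one follow-up visit.

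After the change there are 2 scheduled tests up to and including baseline, the newest sample is 0 days old at the baseline visit, and 1 text gates dispensing. The cost is protocol wording, one form row, one inexpensive assay per affected woman on blood already drawn at baseline, and possibly a short wait before the drug is handed over.

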### **Fasting metabolic parameters**

Patients will be requested to attend the study visit having fasted overnight (for 12 hours).

Definition of fasting: no food, caffeine or caloric drinks; free water is allowed and encouraged. Samples will be sent for TC, HDL, LDL, TG and glucose.

Study participants and site investigators will be blinded to the results of metabolic testing until the completion of the study. This is to prevent self-modification of lifestyle or diet in an attempt to normalise out-of-range results

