#### Randomisation

A computerized random number generator will be used to assign treatment arms. Block Randomisation will be stratified by country.

There will be seven study visits over the 96 week duration of the study.

cIMT, cPWV and biomarkers of immune activation and inflammation will be

measured at screening visit and compared to values obtained after 48 and 96 weeks of treatment with the study medication.

cIMT and cPWV measurements will be performed in duplicate, by the same operator at the AH Heart Centre or the Swiss site, who will remain blinded to participant randomization, throughout the study.

All samples will be processed on site at the AH or the Swiss site. Standard laboratory assessments (i.e. biochemistry, full blood examination (FBE), fasting lipids, hsCRP) will be processed by AH pathology department or the Swiss sites' local laboratories. Markers of innate immunity and inflammation will be performed in the Burnet laboratories. Plasma and PBMCs will be separated from research bloods samples, frozen to -140°C and stored onsite in the Burnet laboratory for possible further analysis in the future.

*For Switzerland: Plasma samples for testing of inflammation markers will be stored on site at minus 80° and shipped to central biobank (sérothèque) HUG for analysis at the HUG cardiology laboratory.*

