### 12.7 Week 24 visit

Participants will be required to present having fasted overnight for at least 12 hours (no food, caffeine or caloric drinks; free water is encouraged)

Assessments performed:

1. Assessment for adverse events
2. Laboratory assessment for:
  - a. Biochemistry
  - b. Fasting metabolic assessment
  - c. HIV Viral load and CD4+ T-cell count (and percentage)

Patients will be provided with a six (6) month supply of the study medication

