### **12.10 Week 96 visit**

Participants will be required to present to the AH having fasted overnight for at least 12 hours (no food, caffeine or caloric drinks; free water is encouraged).

Assessments performed:

1. Targeted physical examination and updated history, assessment for new concomitant medications
2. Weight recorded
3. Compliance assessment
  - a. Self-assessment questionnaire and VAS
4. Adverse event assessment
5. Laboratory assessments
  - a. FBE
  - b. Biochemistry
  - c. Fasting metabolic assessment
  - d. hsCRP
  - e. HIV Viral load and CD4+ T-cell count (and percentage)
  - f. Markers of innate immunity and inflammation
  - g. Storage of plasma and PBMCs (\*Melbourne participants only) for possible further analysis in the future
6. Calculations
  - a. Creatinine clearance
  - b. BMI
7. Structural assessments
  - a. cIMT
  - b. cPWV (\*Melbourne participants only)

Patients will be advised to cease study medication. Statin will be prescribed according to physician's assessment.

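### The blind on fasting metabolic results covers the only scheduled glucose test and has no safety exception, so an asymptomatic high value at week 24 or 48 has no stated route to the site

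*Combined protocol and SAP*

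**What the plan says.** - **What is blinded.** Section 11.2, Fasting metabolic parameters, defines the panel: "Samples will be sent for TC, HDL, LDL, TG and glucose". It then states: "Study participants and site investigators will be blinded to the results of metabolic testing until the completion of the study". The reason given is to stop participants changing diet or lifestyle in response to abnormal results. No threshold or exception follows.
- **When glucose is measured.** The flow chart (section 5) has one glucose row, "Fasting Lipids/glucose", marked at screening, baseline and weeks 24, 48 and 96. Section 12.7 (week 24) lists "Fasting metabolic assessment", and section 12.8 (week 48) has the same item. At week 96 the panel is drawn again, and "Patients will be advised to cease study medication" (section 12.10).
- **What the site does see.** The unblinded biochemistry in 11.2, Laboratory assessments for safety, runs from sodium to "Urea (Ur), Creatinine (Cr) and creatinine phosphokinase (CPK". That list, the liver tests that follow it and flow-chart footnote h all omit glucose.
- **Who runs the test.** Under 11.2, Handling of Biological samples, everything except storage and innate-immunity samples "will be processed at the Alfred Hospital laboratory or the Swiss site". Section 8.1 says the same of standard assessments, which "will be processed by AH pathology department or the Swiss sites" (their local laboratories), although its list of examples does not name glucose.
- **Known risk.** Section 10.8 puts diabetes among the frequent side effects and quotes 2.8% on rosuvastatin against 2.3% on placebo in the cited trial.
- **A parallel blind.** Section 11.3 also withholds carotid results until the end, but releases them if a significant plaque needs clinical attention.

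**The concern.** Glucose is both a secondary efficacy outcome and the laboratory signal for a side effect that the protocol itself lists. The blind treats it only as the former. If the text is followed as written, a participant without symptoms can have a clearly raised fasting glucose at week 24 and be given further supplies of study drug at weeks 24, 48 and 72 without anyone at the site knowing. The site then cannot repeat the test or refer the participant. Nor can it grade the event and judge causality at the time, as section 13 expects for adverse events. The carotid blind shows that the authors accept a clinical exception in principle; the metabolic blind has none.

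**Working it through.** The plan gives no figure to reproduce on this point. The check is mainly textual, with three small calculations.

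**1. Possible routes to the site for an asymptomatic high glucose at week 24 or 48**

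| Route | Section | What it provides |
|---|---|---|
| Safety biochemistry | 5, 11.2 | No glucose |
| Specific adverse event questions | 11 | Muscle and gastrointestinal symptoms, jaundice |
| Laboratory withdrawal triggers | 9.4 | CK and transaminases only |
| Emergency unblinding | 10.11 | Opens the treatment code, not laboratory results |
| Unscheduled visits | 12.11 | Extra safety tests allowed, but someone must have a reason to ask |
| DSMB | 15 | Monthly laboratory-toxicity summary; stated output is a recommendation about the trial |
| Local laboratory | 8.1, 11.2 | Sees the value; no instruction to pass it on |

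None of these states a route for an individual value.

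**2. Time hidden while on drug (nominal schedule, drug stops at week 96)**
- Week 24 value: 96 − 24 = 72 weeks.
- Week 48 value: 96 − 48 = 48 weeks.

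These are maxima on nominal dates; the visit windows in 12.2 can move either end. If completion of the study means the whole project (5 years expected, section 8.2), the results stay closed for longer still, though no longer on drug.

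**3. Scale (assumption: the rates quoted in 10.8 apply here)**
- Per arm: 102 / 2 = 51.
- Rosuvastatin: 51 × 0.028 = 1.43 cases. Placebo: 51 × 0.023 = 1.17 cases.
- Both arms: 1.43 + 1.17 = 2.60. With the full 15% dropout of section 6.6 removed: 2.60 × 0.85 = 2.21. Hence about 2 to 3.
- Excess on rosuvastatin: 51 × (0.028 − 0.023) = 0.26 cases.
- Probability of at least one case among 102: 1 − 0.972^51 × 0.977^51 = 0.93.

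The cited trial differs in population and follow-up. These are also diabetes cases, not glucose values above a threshold, for which the documents give no rate.

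**4. Which threshold gives one rule**
- Upper reference limits: 6.0 mmol/L at Swiss sites (22.4) and 7.7 mmol/L at the Alfred (22.3).
- Fasting grades (22.6): Grade 2 starts at 6.95 mmol/L and Grade 3 at 13.89 mmol/L.
- Order: 6.0 < 6.95 < 7.7 < 13.89.

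A trigger based on each laboratory's own limit would differ by country. Grade 3 would be common to both but misses everything from 6.95 to 13.88 mmol/L. Grade 2 is common to both; its cost is that values from 6.95 to 7.7 mmol/L lie within the Alfred range.

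**The case against.** The strongest reply is that the blind is deliberate and reasoned, and that surrounding care limits the harm. Type 2 diabetes is excluded and glucose is measured at screening. Participants remain in routine HIV care, which may test glucose. Every later visit asks about new diagnoses and medications (section 11), so diabetes found elsewhere reaches the site. Treating physicians are not named in the blind and may initiate unscheduled visits. Much of this stands, and it is why few people are likely to be affected. But these routes depend on chance: the documents neither say that routine care includes glucose nor send the trial result to the treating physician.

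An alert also touches a secondary outcome. Section 7.2 lists fasting glucose and section 17 models it by arm and time, so treatment started after an alert would alter later values. That stands as a cost of the change.

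A reader might infer three stronger things that the documents do not support:
- **That nobody sees the values during the trial.** The laboratories do, and severe values may reach the DSMB through the monthly summary. What is missing is a stated return to the site.
- **That all on-drug results, 102 × 2 = 204, measure the problem.** That counts every glucose result at weeks 24 and 48, most of them presumably unremarkable, and not high values or people.
- **That the comparison of arms, or the trial-level safety assessment, is damaged.** Glucose can still be graded and compared once the blind is lifted.

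**Conclusion.** The point holds as an individual-safety gap in the text available. The only scheduled glucose test is blinded to participants and site investigators without exception, and no stated route carries an asymptomatic high value at week 24 or 48 to the site, nominally for up to 72 or 48 weeks on drug. It probably concerns few people: about 2 to 3 diabetes cases across both arms if the rates in 10.8 carried over, as an order of magnitude only.

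The conclusion rests on two assumptions. The first is that the blind is applied as written after randomisation; it cannot be literal at screening, where eligibility and the Framingham score need the lipid results. The second is that no alert rule exists elsewhere. The consent form was not available, and the separate Swiss laboratory SOP mentioned in 11.2 is not included; either could contain one. It would therefore go too far to say that the trial has no such route at all. This is a cheap improvement worth making, not a flaw that threatens the trial's conclusions.

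**What to change.** Keep post-randomisation lipids blinded. Add to 11.2 that the local laboratory already running the test notifies the site of any post-randomisation fasting glucose of Appendix 22.6 Grade 2 or higher (6.95 mmol/L or above), under the same rule in both arms and both countries, so that the site can repeat the test and manage the participant clinically. If an alert rule already exists in the Swiss SOP or elsewhere, check that it covers both countries and cross-refer to it in 11.2.

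The cost is one added rule in the protocol and an instruction to the laboratories. An alert should say little about allocation: if alerts followed the diabetes rates in 10.8, the chance that a case is on rosuvastatin would be 1.43 / 2.60 = 55%.

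There are two downsides. Some alerts will fall within the Alfred reference range (up to 7.7 mmol/L) and need only a repeat test. A few participants may change lifestyle or start glucose treatment, which gives up a little of the blind's purpose and slightly affects later values of the secondary fasting-glucose outcome. Record any such treatment, and report that outcome with and without post-alert values.
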